### 6.5.1 Analysis Methodology

Freedom from AF will be calculated as the number of subjects without a failure as defined in section 6.5 divided by the total number of subjects in the analysis population. Corresponding exact two-sided 95% binomial confidence intervals will also be calculated.

### 6.5.2 Analysis population

The analysis population for this endpoint will include all enrolled subjects who have also had the TactiCath SE inserted into their vasculature and who have completed their 1-year visit or crossed the 1-year visit window without the visit but with an event as defined above for the descriptive endpoint #5.

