- Consistent with data published in the 2017 HRS/EHRA/ECAS/APHRS/SOLAECE Expert Consensus Statement on Catheter and Surgical Ablation for Atrial Fibrillation, the following standard of care peri-procedure precautions are strongly recommended to minimize risks to subject safety:
  - Esophageal temperature monitoring – it is strongly recommended that esophageal temperature be monitored using an esophageal temperature probe at the anatomical location nearest the site of energy delivery. An alternative is esophageal deviation.
  - Termination of energy is strongly recommended if a >1°C rise in esophageal temperature is observed.

- Intracardiac echocardiography (ICE) – use of a phased-array ICE probe during the procedure to guide septal puncture and to monitor catheter position and manipulation is strongly recommended.
- Use of robotic systems to assist in the procedure is not allowed.
- Please refer to the catheter's IFU for further details.
- PVI must be documented and verified via entrance block with a multipolar catheter at or beyond 30 minutes from the last ablation lesion for each vein.
- Use of adenosine and / or isoproterenol is acceptable to assist in finding gaps.
- Cardioversion is allowed after PVI to assist with checking for isolation.
- The data from the entire procedure recorded on the commercial EnSite system should be anonymized and backed up on a USB drive and sent to the sponsor within reasonable timelines.
- It is strongly recommended that the operator personally evaluates the subject on the evening of the procedure as well as on the following morning, and maintains active surveillance of the subject's postoperative care and condition.

If for any reason the subject has the TactiCath SE inserted into their vasculature, but no ablation is performed, the subject will be followed up for 30 days to assess safety, then exit the trial.

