**Table 2 List of all clinical investigation specific tests and activities**

Study Activity	Enrollment/ Baseline	Procedure (within 14 days of consent)	Pre- Discharge	7-Day Visit (± 2 days)	30-Day Visit (± 7 days)	3-month Visit (± 14 days)	6-month Visit (± 21 days)	12-month Visit (± 21 days)
Eligibility Check	X							
Informed Consent Process	X							
Demographics / Medical History	X							
Physical Examination (including neurological assessment)	X		X	X				
NIHSS	X		X	X				
Diffusion-weighted MRI - Brain	(X)		(X)	(X)				
CT or MRI of pulmonary veins				(X)	(X)		(X)	(X)
Urine pregnancy test	(X)							
NYHA	X							
Record Antiarrhythmic / Anti- coagulant Medication	X		X	X	X	X	X	X
Confirm absence of thrombus (per standard of care)**	X	(X)						
Ablation procedure		X						
Trans thoracic echocardiogram		X*						
Trans telephonic monitoring***						X	X	X
12-Lead ECG	X				X	X	X	X
24-hour Holter-monitoring								
QOL (EQ-5D-5L & AFEQT)	X					X	X	X
Adverse Events	(X)	(X)	(X)	(X)	(X)	(X)	(X)	(X)
Deviation	(X)	(X)	(X)	(X)	(X)	(X)	(X)	(X)
Withdrawal	(X)	(X)	(X)	(X)	(X)	(X)	(X)	(X)
Health Care Utilization				(X)	(X)	(X)	(X)	(X)

(X) if applicable

\*Recommended post procedure to exclude pericardial effusion.

\*\*Must be done within one day of procedure (day of or day prior to).

\*\*\*Collected monthly and whenever symptoms are present from 3 to 12 months post ablation procedure.

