##### 6.1.7.2 Analysis Population

The analysis population for this endpoint will include all enrolled subjects who have also had the TactiCath SE inserted into their vasculature and who have completed their 1-year visit or crossed the 1-year visit window without the visit but with an event as defined above for the descriptive endpoint #5. In addition, the analysis will be run on the subset of subjects who also meet descriptive endpoint #2 (achieving  $\geq 10$ g contact force).

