### 5.1.4 Analysis Population

The analysis population for this endpoint will include all enrolled subjects who have also had the TactiCath SE inserted into their vasculature, and either had an event or completed a visit at or beyond their 30-day follow up visit window. Subjects without an event that are lost to follow up without a visit at or beyond their 30-day follow up visit window will be excluded from this analysis.

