### **5.1.6 Sensitivity Analysis**

To demonstrate robustness with respect to missing data, a tipping point analysis will be performed for the primary safety endpoint. This will involve imputing all possible combinations of outcomes for the primary endpoint among subjects who terminate the study prematurely without experiencing any primary safety endpoint events.

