### 6.5.3 Subgroup Analysis

The following subgroups will be evaluated for the analysis population as defined in section 6.5.2.

- Subjects who also meet descriptive endpoint #2 (achieving  $\geq 10g$  contact force)
- Achieving  $\geq 90\%$  lesions with  $\geq 10g$  contact force (Yes vs No)
- Agilis (Yes vs No)

For the comparison between two subgroups, the analysis might be performed if there are at least 30 subjects in each group. Analysis will be based on Fisher's exact test.

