### 6.6.2 Analysis Population

The analysis population for this study will be based on all subjects in whom a study device was introduced and who have completed their 1-year visit or crossed the 1-year visit window without the visit but with an event as defined above for the descriptive endpoint #6.

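### One-year success (descriptive endpoints #5 and #6): a subject without the 1-year visit is counted only if an event occurred, and no missing-data check is planned

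*SAP*

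**What the plan says.** SAP 6.5.2 limits the #5 population to subjects with the catheter inserted who attended the 1-year visit or who "crossed the 1-year visit window without the visit but with an event as defined above for the descriptive endpoint #5". SAP 6.6.2 does the same for #6: "crossed the 1-year visit window without the visit but with an event as defined above for the descriptive endpoint #6". Protocol 6.1.7.2 agrees ("completed their 1-year visit or crossed the 1-year visit window without the visit but with an event"), as does Protocol 6.1.8.2. SAP 6.5.1 and 6.6.1 define the estimate as a plain proportion, subjects without failure over the analysis population, with an exact two-sided 95% interval.

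A failure can be known without the 1-year visit, because the Table 2 footnote on trans telephonic monitoring reads "Collected monthly and whenever symptoms are present from 3 to 12 months post ablation procedure". The 24-hour Holter, however, is done only at the 12-month follow-up, which also has its own 12-lead ECG (Protocol 5.3.4).

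The primary safety population has a similar form: subjects who "either had an event or completed a visit at or beyond their 30-day follow up visit window" (SAP 5.1.4). There the SAP adds a safeguard: "a tipping point analysis will be performed for the primary safety endpoint" (SAP 5.1.6). SAP 6.5 and 6.6 contain a definition, methodology, population and subgroups, and nothing on missing data. For the one-year adverse-event endpoint #4, SAP 6.4.1 treats early leavers without an event as event-free.

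**The concern.** Among subjects without the 1-year visit, only failures reach the denominator. If missing the visit has nothing to do with outcome, this adds failures without the matching successes and lowers the reported rate. If the subjects who leave are those doing worse, dropping the event-free leavers can raise it. The planned exact interval covers sampling error only and shows neither effect.

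The phrase about crossing the 1-year window adds a second uncertainty. A subject with a documented recurrence at month 5 who withdraws at month 6 might be counted (reading A) or not (reading B). Two analysts could report different rates from the same data.

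At stake is how the one-year rates are read, and any subgroup comparison built on the same counts. For those, SAP 6.5.3 says "the analysis might be performed if there are at least 30 subjects in each group", using Fisher's exact test.

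**Working it through.** **Inputs.** The denominator rule and estimator are as described. The visible text gives no expected success rate, dropout rate or sample size for #5/#6, so there is no plan figure to reproduce. Blacked-out sample-size text is not held against the plan. Assumed values: true 12-month success S of 60, 70, 80 or 90%; share m without the 1-year visit of 5, 10 or 15%; constant failure hazard from day 90 to day 365.

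**Formula.** Let q be the probability that a subject without the visit enters the denominator as a failure. If missingness is unrelated to outcome, the expected reported rate is E = S(1-m) / [(1-m) + mq].

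**1. Only the visit is missed and every failure is known: q = 1-S.**

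| S, m | E | Shift (points) |
|---|---|---|
| 90%, 5% | 0.855/0.955 = 89.53% | -0.47 |
| 70%, 10% | 0.630/0.930 = 67.74% | -2.26 |
| 60%, 15% | 0.510/0.910 = 56.04% | -3.96 |

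The first and last rows are the extremes of the grid.

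**2. A share f of failures would be found only at the 12-month visit: q = (1-f)(1-S).** The values of f are assumed.
- 70%, 10%: f = 25% gives 0.630/0.9225 = 68.29% (-1.71); f = 50% gives 0.630/0.915 = 68.85% (-1.15).
- 60%, 15%: f = 25% gives 0.510/0.895 = 56.98% (-3.02); f = 50% gives 0.510/0.880 = 57.95% (-2.05).

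Case 1 is therefore an upper limit on the downward shift.

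**3. Dropout uniform over days 0-365, unrelated to outcome.**
- Reading A: q = (275/365)[1 - (1-S)/(-ln S)]. At S = 70%, q = 0.1197, so at m = 10% E = 0.630/0.91197 = 69.08% (-0.92). The grid runs from -0.18 to -1.68.
- Reading B: q = 0, so E = S and there is no shift.

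**4. Subjects with missing data fail at twice the hazard (assumed).** Let s be success among the others. Success among those missing is then s², and (1-m)s + ms² = S fixes s.
- Reading B: E = s. At 90%, 5%, s = 90.43% (+0.43); at 60%, 15%, s = 63.48% (+3.48).
- Reading A: q = (275/365)[1 - (1-s²)/(-2 ln s)]. At 60%, 15%, q = 0.2585 and E = 0.85 × 0.6348 / (0.85 + 0.15 × 0.2585) = 60.71% (+0.71). The grid runs from +0.10 to +0.71.
- Visit missed, failures known (q = 1-s²): -0.43 to -2.60.

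**5. Bounds, illustrative counts.** Take 140 inserted, 2 of them not ablated and 138 ablated. Of the 138, 14 are event-free without 12-month status, and 87 of the remaining 124 are successes.
- Reported under the rule: 87/124 = 70.2%.
- Worst case: 87/138 = 63.0%. Best case: (87+14)/138 = 73.2%.
- Counting the 2 non-ablated subjects as failures would lower the worst case to 87/140 = 62.1%. They leave at 30 days by design, so they are kept out.
- For scale, the exact 95% interval for 98/140 (70.0%) is 61.7 to 77.4%.

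**6. Kaplan-Meier as an alternative.** The 12-month window is 365 ± 21 days, that is days 344 to 386. Suppose true success is 70%, nothing is missing, visits are uniform over the window, a share f of failures is found at the visit, and the rest are recorded before day 344. Event-free subjects are censored at their visit. Put p = 0.3f/(0.7+0.3f). When a fraction r of visits is still to come, the estimate is about (0.7+0.3f) × r^p.
- Read at day 365 (r = 0.5): f = 10, 25 and 50% gives 70.9, 72.5 and 75.2%, which is too high by about 0.9, 2.5 and 5.2 points.
- Read near day 386 the risk set empties. At f = 25% and r = 0.01, 0.775 × 0.01^0.0968 = 49.6%, far too low.

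A Kaplan-Meier estimate therefore helps only if the visit window is handled explicitly.

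**The case against.** The other side has a good case. #5 and #6 carry no hypothesis test and support no labeling claim, the rule is prespecified, and Protocol and SAP agree on it. It also has a rationale. Someone who misses the 12-month visit has not had the Holter and cannot be called a success on equal terms, whereas a documented failure is already final. The largest modelled shift is about half the half-width of the exact interval for 98/140 (7.9 points), and the illustrative bounds fall inside that interval. Counts will be reported and SAP 6.13 summarizes withdrawals, so a reader could work out rough bounds.

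All of that limits the weight of the point. It does not remove the outcome dependence, nor the open question about failures who withdraw early. Withdrawal summaries also do not identify subjects who stayed in the trial but missed the visit.

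Three stronger readings are tempting and are not supported:
- A reader might infer that the rule flatters the device. The direction depends on who is missing and on which reading is applied; with missingness unrelated to outcome the shift is downward or nil.
- A reader might take 4 points as the expected error. That figure needs 60% success, 15% missing and every failure known without the visit.
- A reader might extend the criticism to primary safety because its population has a similar form. That endpoint has a tipping point analysis.

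**Conclusion.** The point holds as a minor one. The #5/#6 denominator depends on outcome among subjects without the 1-year visit, its wording allows two readings for early failures who withdraw, and no visible missing-data check covers either endpoint. With 60-90% success and 5-15% missing at random, the downward shift is at most 0.5 to 4.0 points. It is smaller where some failures would surface only at the 12-month Holter or ECG. If subjects with missing data fail at twice the hazard and leave early, the shift is upward: 0.1 to 0.7 points under reading A and 0.4 to 3.5 under reading B. All these rates are assumptions, because the documents give none. The primary endpoints and the trial success criterion are not affected.

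**What to change.** 1. Beside the planned proportion for #5 and #6, report best- and worst-case bounds (or a tipping point analysis) over all ablated subjects with unknown 12-month status, with the number excluded. Report separately those with insertion "but no ablation is performed, the subject will be followed up for 30 days to assess safety, then exit the trial" (Protocol 5.3.2).
2. State in SAP 6.5.2 and 6.6.2 and Protocol 6.1.7.2 and 6.1.8.2 that a subject with a documented failure who withdraws before the 1-year window is in the denominator, and show the result under the other reading as well.
3. Optional: add a Kaplan-Meier estimate from the end of blanking, labelled as assuming non-informative censoring. Assign failures found at the 12-month visit to the nominal 12-month time, with event-free attenders censored at that same time after the failures. If it is read at day 386 instead, event-free attenders must stay in the risk set until day 386, for the reason shown in step 6 of the working.

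The cost is a wording change in both documents and a few extra report rows, with no new data collection. The downside is a possibly less favourable reported range.

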### 6.5.3 Subgroup Analysis

The following subgroups will be evaluated for the analysis population as defined in section 6.5.2.

- Subjects who also meet descriptive endpoint #2 (achieving  $\geq 10g$  contact force)
- Achieving  $\geq 90\%$  lesions with  $\geq 10g$  contact force (Yes vs No)
- Agilis (Yes vs No)

For the comparison between two subgroups, the analysis might be performed if there are at least 30 subjects in each group. Analysis will be based on Fisher's exact test.

## 6.6 Descriptive Endpoint #6

Descriptive endpoint #6 is one-year drug-free success, defined as freedom from any AF/AFL/AT lasting at least 30 seconds or any Class I or III AAD after removal from antiarrhythmic drug therapy as assessed from the end of the 3-month blanking period to 12 months following the ablation procedure.

A full 10-second 12-lead ECG recording of arrhythmia may be substituted for a 30-second recording unless there is evidence that the recorded arrhythmia is short-lived and less than 30 seconds.

### 6.6.1 Analysis Methodology

Freedom from AF will be calculated as the number of subjects without a failure as defined in section 6.6 divided by the total number of subjects in the analysis population. Corresponding exact two-sided 95% binomial confidence intervals will also be calculated.

### 6.6.2 Analysis Population

The analysis population for this study will be based on all subjects in whom a study device was introduced and who have completed their 1-year visit or crossed the 1-year visit window without the visit but with an event as defined above for the descriptive endpoint #6.

### 6.6.3 Subgroup Analysis

The following subgroups will be evaluated for the analysis population as defined in section 6.6.2.

- Subjects who are also off of antiarrhythmic medication at the end of the blanking period.
- Subjects who also meet descriptive endpoint #2 (achieving  $\geq 10g$  contact force).
- Achieving  $\geq 90\%$  lesions with  $\geq 10g$  contact force (Yes vs No)
- Agilis (Yes vs No)

For the comparison between two subgroups, the analysis might be performed if there are at least 30 subjects in each group. Analysis will be based on Fisher's exact test.

## 6.7 Descriptive Endpoint #7

Descriptive endpoint #7 is change in EQ-5D-5L scores from baseline to follow up at 3, 6, and 12 months.

### 6.7.1 Analysis Methodology

Changes in EQ-5D-5L score between baseline and follow up visits will be summarized with descriptive statistics. Scores will be used to calculate utility values and QALYs.

### 6.7.2 Analysis Population

The analysis population for this endpoint will include all enrolled subjects who have also had the TactiCath SE inserted into their vasculature, have a baseline EQ-5D-5L, and who have completed their applicable follow up visit.

## 6.8 Descriptive Endpoint #8

Descriptive endpoint #8 is change in AFEQT scores from baseline to follow up at 3, 6, and 12 months.

### 6.8.1 Analysis Methodology

Changes in AFEQT between baseline and follow up visits will be summarized with descriptive statistics to assess change in functional improvement.

### 6.8.2 Analysis Population

The analysis population for this endpoint will include all enrolled subjects who have also had the TactiCath SE inserted into their vasculature, have a baseline AFEQT, and who have completed their applicable follow up visit.

## 6.9 Descriptive Endpoint #9

Descriptive endpoint #9 is cardiovascular-related health care utilization through 12 months post index ablation.

### 6.9.1 Analysis Methodology

Descriptive statistics will be generated for all variables.

### 6.9.2 Analysis Population

The analysis population for this endpoint will include all enrolled subjects who have also had the TactiCath SE inserted into their vasculature and who have health care utilization data available.

## 6.10 Descriptive Endpoint #10

Descriptive endpoint #10 is force time integral (FTI) and lesion index (LSI).

### 6.10.1 Analysis Methodology

FTI and LSI will be derived from the from the available Ensite Precision data. Descriptive statistics will be generated for both variables.

### 6.10.2 Analysis Population

The analysis population for this endpoint will include all enrolled subjects who have also had the TactiCath SE inserted into their vasculature.

### **6.11 Baseline and Demographic Characteristics**

Descriptive statistics of continuous variables will be presented and will include number of subjects, mean, median, standard deviation, minimum and maximum. For categorical variables, the number and percentage of subjects in each category will be presented as appropriate. Baseline characteristics will be tabulated. As needed and appropriate, categorical variables will be tested using Fisher's exact test and continuous variables will be tested using two sample t-test.

### **6.12 Mortality**

The number and causes of deaths will be summarized.

### **6.13 Withdrawal**

Withdrawal from the study and reasons for withdrawal will be summarized.

### **6.14 Protocol Deviation**

Protocol deviations will be summarized for subjects in whom protocol deviations are reported.

There is no plan to deviate from this Statistical Analysis Plan. If any deviations from the original statistical plan occur, such deviations will be documented in the clinical study report or statistical report containing the analysis results.

**7 REVISION DESCRIPTION****[REDACTED]**
